Research methods: In this study, the split-body design was adopted as an experimental study of random assignment, and the four parts of the patient's body that were in contact with the positioning device (left chest, left iliac crest and right chest, right iliac crest) were randomly assigned to In the experimental group or the control group, compare the decompression effect of different materials on the positioning device on the patient; the experimental group uses the positioning device ReltonHall prone frame 3 cm cotton roll-coated viscoelastic polymer pads, and the control group uses the positioning device ReltonHall prone frame viscoelastic polymer pads. The research object is lumbar surgery patients in the operating room of a hospital in the north. It is expected to enroll 50 people. The experimental group or the control group will be assigned by random number table. the measurement time is before operation, immediately after operation, 30 minutes after operation, 24 hours after operation, and 48 hours after operation. This study uses SPSS 25.0 Chinese version package software for data analysis, descriptive statistics use frequency, percentage, average value, standard deviation, etc., and inferential statistics use independent sample t test, chi-square test, generalized estimating equation, etc. to analyze data.

Keywords: lumbar spine surgery, pressure injury, positioning device, preventive, split design

II. the content of the plan

1. Research background:Please describe the background and importance of this plan. The content can be written with reference to the following points: (1) Policy or Legislative basis (2) Problem situation or development requirements (3) Literature research on related research at home and abroad or this plan (4)Relevance of health care. (page limit 5 pages)

Research background and motivation

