lack of narrative. For a plan with a period of more than one year, the overall goal of the whole plan and the plans for each year should be listed
purpose. (page limit 2 pages)

Research purposes

For patients undergoing spinal posterior surgery (spinal posterior surgery), the decompression material of the intraoperative positioning device (Relton-Hall prone frame) is used to wrap the fat pad and fat pad material with cotton rolls. Is there a difference in the rate.

3. Test object: The content includes the following points for writing: (1) Inclusion and exclusion conditions (2) Number of subjects (3) Recruitment sources and methods (4) Protection of research subjects' rights and methods of informed consent. (page limit 5 pages)

research object

Patients with lumbar spine surgery in the operating room of a hospital in the north are eligible for inclusion as follows:

1. Patients who underwent lumbar nerve decompression combined with internal fixation and bone fusion.
2. Take the prone position using the ReltonHall rack.
3. The operation time is greater than 2.5 hours.
4. The surgical anesthesia is general anesthesia.
5. Routine surgery registered in the surgery schedule.
6. Before the operation, the skin was intact and there was no pressure injury.

Exclusion criteria as follows:

1. Patients undergoing emergency lumbar surgery.
2. Are younger than 18 years old.
3. The operation time is less than 2.5 hours.
4. Preoperative skin incompleteness (obvious chest and iliac crest pressure phenomenon).
5. Percutaneous minimally invasive disc herniation decompression (percutaneous endoscopic lumbar disc, PELD).

Sample Size Estimation

The author refers to the research results of Yang et al. (2020) to estimate the sample size, estimates with G-power 3.1 software, sets the significance level of α value to 0.05, and the test power is 0.80, using the ratio of two groups (chi-square test) To test the sample size, the minimum sample size for this study was determined to be 93 people. According to the estimated number of samples and pre-test results in the above literature, it is planned to collect 93 people. After correcting the sample loss rate, 100 people will be recruited. Since this study adopts a split test (self-experimental group and control group), it is estimated that Enroll 50 people.

research ethics

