To follow the principles of patient autonomy, non-injury and confidentiality, before the research is conducted, the purpose and process of the research must be explained to the research subjects or their families, and the patients can request to stop at any time during the research process without affecting the future medical rights and safety. Before the implementation of this study, it is expected to be submitted to the Human Research Ethics Committee of a medical center in central China for review; the data of the research subjects will only be used for academic research to protect the privacy of the research subjects.

4. Research method:The content includes the following points for writing: (1) The standard and number of subjects to be tested (2) The design and method of the test (3) The duration and progress of the test (4) Tracking or rehabilitation plan (5) Evaluation and statistical methods (6)) Tracking of subjects and necessary care plans.

Research design

This study adopts the split-body design (left chest, left iliac crest and right chest, right iliac crest) as an experimental study, comparing two kinds of decompression materials (positioning device ReltonHall prone frame The effect of wrapping the fat pad with a cotton roll on one side and the fat pad on the other side) in reducing pressure injuries. The split design is that each patient is an experimental group and also a control group to remove biological variability, such as demographic characteristics: potential factors such as gender, age, disease history, nutritional status, and overall health status. It is expected to understand the effect of the ReltonHall cotton roll-coated fat pad and the fat pad on the incidence of postoperative pressure injury and the decompression effect of patients undergoing lumbar spine surgery.

Research Design Patterns

group	Pretest	intervention	Posttest I immediately	Posttest II 30 minutes	Posttest III 24 hours	Posttest IV 48 hours
Experimental side	O1	X1	O2	O3	O4	O5
control side	O1	x	O2	O3	O4	O5

Note:

O1: After general anesthesia, the subject was placed supine to measure the integrity of the skin.

X1: Refers to the experimental side chest and iliac crest positioning device ReltonHall fat pad wrapped cotton roll 3 cm.

X: Refers to the ReltonHall, the positioning device of the chest and iliac crest of the control group, which is the fat pad routine.

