O2: Immediately after the operation, I was measured after the pressure injury was graded on the experimental side and the control side.

O3: 30 minutes after the operation, the experimental side and the control side were tested for pressure injury grade II.

[figure not shown]
O4: 24 hours after the operation, the experimental side and the control side were tested for pressure injury grade III.

O5: 48 hours after the operation, test the IV after the pressure injury grade was carried out on the experimental side and the control side.

Positioning and intervention methods

The patient enters the operating room, and the four support cushions on the frame have been disposed in advance according to the experimental side and the control side. After general

anesthesia, the surgical team uses standard positioning steps to measure the body length: from the 2 cm mark point of the armpit to the iliac side. between the bony crests; and body width: between the two iliac crests, then adjust the patient's posture and the contact surface of the prone frame according to the markings on the ReltonHall prone frame support pads to ensure that the pressure points on the patient's body are consistent with the marked points; place the patient Lie prone on the ReltonHall prone frame. After the patient is in the prone position, the horizontal line between the scapula and the posterior iliac crest must be parallel to the ground.

1. Experimental side intervention method

Viscoelastic polymer pads (Viscoelastic Polymer Pads) (model 40700; Action, Hagerstown, MD) were used on the 4 support columns of the Relton-Hall prone frame of the positioning device. The dimensions were: 18 cm long, 15 cm wide, and 2 cm thick. The fat pad accessories are designed to cover the four support columns of the Relton-Hall prone frame. The fat pad of the chest and iliac crest on the same side on the Relton-Hall prone frame is covered with a cotton roll for 3 cm. The skin is the experimental side.

2. Control Side Intervention Method

In addition to the experimental side, the fat pad of the chest and iliac crest on the other side of the Relton-Hall prone frame, and the patient's skin contact position is the control side.

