Pressure injury record form, this record form is based on the wound evaluation indicators jointly developed by the National Pressure Ulcer Advisory Committee (NPIAP, 2016) and the European Pressure Ulcer Advisory Panel (EPUAP), according to the established Designed according to pressure injury grading standards.

According to this record sheet, the recorded pressureing conditions are divided into "pre-operative assessment", "immediately post-operative assessment", "30-minute post-operative assessment", "24-hour post-operative assessment", and "48-hour post-operative assessment". Nursing staff in the ward and wards should evaluate and record the pressure points that may cause pressure injuries. Including the site of occurrence and the grade of pressure injury. In order to increase the accuracy of the evaluation, the classification and description of the pressure injury are provided at the bottom of each record sheet for reference.

Statistical analysis methods for various data

data item	Statistical analysis method
1. Basic information of subjects: 1. Gender, age, suffering from chronic diseases, BMI, operation time, albumin, intraoperative body temperature, and intraoperative blood pressure.	1. Described in terms of times, percentages, etc. 2. Chi-square was used to test whether there was a significant difference between the experimental group and the control group.
2. Age, days of pressureing.	1. Described by means, standard deviations, etc. 2. Independent sample t test was used to test whether there was a significant difference between the experimental group and the control group.
2. The pressured parts of the two groups of subjects (one-sided chest, iliac crest), whether there is PI in the compressed parts of the two groups, the contact point of one-sided chest and iliac crest (experimental group), the other side of the chest, The contact point of the iliac crest is (control group)	Independent sample t was used to test whether there were significant differences between the experimental group and the control group immediately after operation, 30min, 24hr, and 48hr.

3. To test whether there are significant differences due to time factors between the two groups of subjects under the decompression material immediately after the operation, 30min, 24hr, and 48hr.

Test the experimental group and the control group by the generalized estimating equation

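### The baseline tests compare the same 50 patients with themselves, and days of pressure gets an unpaired t test in a paired design

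*Protocol*

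**What the plan says.** **Design.** Section 4 of the protocol, under Research design, states that "each patient is an experimental group and also a control group to remove biological variability", and names gender, age, disease history, nutritional status and general health as factors removed in this way. The paragraph on the experimental side makes the comparison one side against the other: "The fat pad of the chest and iliac crest on the same side on the Relton-Hall prone frame is covered with a cotton roll", with the pads on the opposite side as control. Sample Size Estimation halves 100 people to 50 because each person supplies both groups.

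**Analysis.** The first item of the statistical analysis table has two rows.

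- Row 1 covers "Basic information of subjects: 1. Gender, age, suffering from chronic diseases, BMI, operation time, albumin, intraoperative body temperature, and intraoperative blood pressure". After counts and percentages it plans: "Chi-square was used to test whether there was a significant difference between the experimental group and the control group".
- Row 2 covers "Age, days of pressureing". After means and standard deviations it plans: "Independent sample t test was used to test whether there was a significant difference" between the same two groups. Age thus appears in both rows, under two different tests.

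The Summary lists the methods overall: "inferential statistics use independent sample t test, chi-square test, generalized estimating equation, etc. to analyze data".

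**The concern.** These are the baseline comparisons of a parallel trial with two separate sets of patients. Here there is one set of patients, each counted in both groups. A patient's sex, albumin or operation time is the same whichever side is considered, so the tests cannot detect anything. A baseline table built this way would present one cohort as two and report p-values that do not depend on the data.

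Days of pressure is different, because its unit is not stated. If it is recorded per side, it is an outcome that can differ between sides, and an unpaired test discards the within-patient pairing that the design was chosen to provide. This is the only place in the item where a reported result could change.

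**Working it through.** The protocol states no figure for these tests, so there is none to reproduce. The one input is its sample size: 100/2 = 50 patients, hence 50 sides per group.

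**1. Chi-square on a patient-level variable.** Let a_j be the number of patients in category j. Both groups contain a_j.
- Expected count in each cell: 50 × 2a_j / 100 = a_j, which equals the observed count.
- Chi-square = Σ(O − E)²/E = 0, so p = 1.
- Example, 10 with and 40 without a condition: expected 50 × 20/100 = 10 and 50 × 80/100 = 40, so chi-square = 0. Splits of 25/25 and 33/17 give the same.
- If all 50 fall in one category, the other category has an expected count of 0 and the statistic is undefined.

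**2. Independent t test on age.** Both groups have the same mean, so the difference is 0. This gives t = 0, df = 50 + 50 − 2 = 98, p = 1.

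**3. Days of pressure, one value per patient.** As in step 2: t = 0, p = 1.

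**4. Days of pressure, one value per side.** Let both sides have variance σ², with within-patient correlation rho and n pairs.
- Standard error used by the independent test: sqrt(2σ²/n).
- Correct standard error for the paired difference: sqrt(2σ²(1 − rho)/n).
- Ratio: 1/sqrt(1 − rho), whatever n is and without assuming normality.

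The protocol gives no rho. The table shows a range of assumed values. Size and power come from 20,000 simulated trials of 50 normally distributed pairs, two-sided 5% level, with an assumed true difference of 0.4 SD for power.

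| Assumed rho | SE ratio | Type I error, unpaired | Type I error, paired | Power, unpaired | Power, paired |
|---|---|---|---|---|---|
| 0 | 1.00 | 5.1% | 5.0% | 51% | 50% |
| 0.3 | 1.20 | 2.2% | 5.1% | 51% | 65% |
| 0.5 | 1.41 | 0.6% | 5.0% | 51% | 79% |
| 0.7 | 1.83 | 0.05% | 4.8% | 52% | 95% |

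Days counted up to 48 hours would be few and discrete, not normal. A check with values of 0, 1 or 2 days shows the same direction. With an assumed 30% of sides injured, split equally between 1 and 2 days, the unpaired test has true size 5.0%, 2.9%, 1.5% and 0.4% at rho 0, 0.20, 0.36 and 0.54. The paired t test stays at about 5%.

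**5. If the four sites were allocated one by one.** The allocation sentence in the Summary, read alone, allows this. Under independent 1:1 allocation:
- P(all four sites in one group) = 2/16 = 12.5%, or 50 × 0.125 = 6.25 patients expected.
- The other 87.5% of patients are in both groups.
- P(two sites in each) = 6/16 = 37.5%, so 62.5% of patients would contribute unequal numbers of sites.

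The two lists would no longer be identical, but they would still consist largely of the same people. Tests for independent groups still would not fit.

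**The case against.** The strongest reply is that nothing important depends on this. A column of p = 1 would be obvious to any analyst, the treatment comparison is untouched, and the same rows already provide the descriptive statistics. That is right and keeps the point minor. It does not make the planned tests meaningful.

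A second reply is that the part with possible consequences is uncertain. Days of pressure sits under basic subject information next to age, the record form is described as capturing site and grade without duration, and the stated aim concerns a rate. The variable may well be one value per patient, and its definition could properly be left to another document. This is fair, and the loss of power shown above is conditional. But the protocol does name a test for the variable, and if there is one value per patient that test is empty.

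Third, a value per site (chest and iliac crest separately) is also possible, and a simple paired test would not handle two sites per side. This stands, and the fix allows for it.

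Fourth, the Summary's method list is open-ended and includes generalized estimating equations, which handle correlated data. These are assigned to the time comparison in item 3, however, and not to this item, where the independent t test is specified by name.

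**Conclusion.** The point holds and is minor. With one side set against the other, the tests of all eight patient characteristics are fixed in advance at a statistic of 0 and p = 1, or are undefined. They contradict the protocol's own reason for choosing the design, but they do not bias the comparison of injury rates.

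The independent t test for days of pressure is unsuitable on every reading: empty if per patient, and blind to the within-patient clustering if per side or per site. In the per-side case, with positive correlation, the error is conservative and a real difference between sides could be missed. Its size rests on an assumed correlation and equal variances. The power figures also assume a 0.4 SD difference and normal data. None of these values is in the protocol.

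**What to change.** - Delete the between-group tests of patient-level variables from both rows. Describe the 50 patients once, with counts and percentages for categorical variables and mean and SD for continuous ones. List age once.
- Define days of pressure and state whether it is recorded per patient, per side or per site.
  - Per patient: describe only.
  - Per side: use a paired t test, or Wilcoxon signed-rank if the differences are skewed or mostly zero.
  - Per site: combine the two sites into one value per side first, or use a method that clusters by patient.
- State how uninjured sides count. If duration exists only for injured sides, the protocol's 5% to 66% incidence, taken per side as an assumption, gives 0.05 × 50 = 2.5 to 0.66 × 50 = 33 sides per group. A paired test would drop every patient without a value on both sides.
- Optionally, report how many patients had the cotton roll on the left and how many on the right.

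The cost is an edit to two table rows and a short definition. No extra patients, visits or measurements are needed.

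### Treatment and sample size go by side, but analysis item 2 words the outcome by contact point; the unit, and so the error rate and the PI rate, is left open

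*Protocol*

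**What the plan says.** **Treatment goes by side.** Under the experimental side intervention method (Protocol, section 4), "The fat pad of the chest and iliac crest on the same side on the Relton-Hall prone frame" is what receives the cotton roll. The other side keeps the pad alone. The research design table has one row for the experimental side and one for the control side, and its notes O2 to O5 grade injury on those two sides.

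**Sample size goes by side.** Under Sample Size Estimation, "the minimum sample size for this study was determined to be 93 people". Then "After correcting the sample loss rate, 100 people will be recruited", and finally "Since this study adopts a split test (self-experimental group and control group), it is estimated that Enroll 50 people". One patient therefore supplies two units, one per arm.

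**The outcome is worded by part.** In the table of statistical analysis methods, item 2 asks whether PI is present in the compressed parts of the two groups. It describes the experimental group as "the contact point of one-sided chest and iliac crest (experimental group" and the control group as the same two points on the other side. The test is an independent-sample t test at each of four readings. The record form captures the site and grade of each injury, so the data arrive by point.

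**Allocation is worded two ways.** The research methods paragraph of the summary says that the four contact areas, listed as left pair and right pair, were randomly assigned. Section 4 puts both areas of a side on one material.

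**The concern.** Each side has two contact points, and both points always receive the same material. They also share that side's load and belong to one patient. Two such points are not two independent pieces of evidence about the pad.

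Item 2 is where the unit of the main comparison is fixed, and it names parts and points. An analyst could reasonably enter 100 points per group into the t test, although the trial was sized on 50 sides per group. Two things then change: the true error rate of the test, and the PI rate itself, because a rate per point and a rate per side are different quantities. PI incidence is the study's stated outcome, so its denominator has to be clear.

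This is separate from the use of an unpaired test on left-right data. Pairing chest with chest and iliac crest with iliac crest would deal with the pairing and still treat a patient's two pairs as independent.

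**Working it through.** **1. The plan's own count.** Sample Size Estimation "sets the significance level of α value to 0.05, and the test power is 0.80", "using the ratio of two groups (chi-square test"). The minimum of 93 cannot be reproduced, because no rates or effect size are given. As a chi-square total with 1 degree of freedom, it corresponds to w of about 0.29 (w = 0.29 gives 94, w = 0.30 gives 88). The later steps do reproduce: 1 − 93/100 = 0.07, so a loss of about 7% is implied; 93/(1 − 0.07) = 100; and 100/2 = 50 patients. That is two units per patient, which are sides. Contact points would be four per patient.

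**2. Number of units.** By side: 50 per group. By contact point: 2 × 50 = 100 per group, 200 in all.

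**3. Error rate of the planned test if points are entered.** Let σ² be the variance of one point's result, rw the correlation of the two points on one side, and rc the correlation between points on opposite sides of a patient. With n patients:

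- Variance assumed by the independent t test: σ²/(2n) + σ²/(2n) = σ²/n.
- True variance: the sum of two points on a side has variance 2σ²(1 + rw), and the two sums have covariance 4rc σ². The difference of group means therefore has variance [4σ²(1 + rw) − 8rc σ²]/(4n) = σ²(1 + rw − 2rc)/n.
- Ratio of true to assumed variance: **1 + rw − 2rc**.
- True type I error at nominal 5%: 2[1 − Φ(1.96/√ratio)].

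The protocol gives neither correlation, so the values below are assumptions.

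| rw | rc | ratio | true type I error |
|---|---|---|---|
| 0.5 | 0.1 | 1.3 | 8.6% |
| 0.3 | 0.1 | 1.1 | 6.2% |
| 0.5 | 0.3 | 0.9 | 3.9% |
| 0.3 | 0.3 | 0.7 | 1.9% |

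The error is above 5% when rw > 2rc and below it when rw < 2rc. More extreme assumptions widen the range: 11.0% at rw 0.5, rc 0, and 0.6% at rw = rc = 0.5.

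**4. Check by simulation** (50 patients, no true difference, 20% PI per point, 20,000 runs per setting):

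| rw, rc | points, unpaired t | sides, unpaired t | any PI per side, paired |
|---|---|---|---|
| 0.30, 0 | 8.4% | 4.9% | 5.3% |
| 0.29, 0.11 | 6.0% | 3.3% | 5.0% |
| 0.30, 0.29 | 2.0% | 1.2% | 4.4% |

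A further simulation at 30% per point gave 2.2% to 7.9% for unpaired points, 1.4% to 4.0% for unpaired sides, and 4.7% to 5.5% for one any-PI result per side compared within patient.

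**5. PI rate by unit.** With rate p per point, the rate of any PI on a side is 2p − p² − rw·p(1 − p).

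- p = 30%: 0.51 − 0.21rw, which is 46% at rw = 0.24 and 41% at rw = 0.48.
- p = 10%: 0.19 − 0.09rw, which is 19% at rw = 0 and 14.5% at rw = 0.5.

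The two rates agree only if rw = 1.

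**The case against.** The strongest reply is that item 2 never says points are counted as independent. Its wording can be read as a label: the chest and iliac contact points together define each side, as they do in the design notes. Separate chest and iliac comparisons are a third reading. This stands, and it limits the point: the text permits pooling but does not prescribe it. A reader might infer that the trial will analyse 200 independent observations, but that figure appears nowhere in the protocol.

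A reader might also infer that the false-positive risk must rise when one side is loaded more than the other. That does not hold for the planned test. Clustering within a side pushes the error up, ignoring the left-right pairing pushes it down, and the net is 1 + rw − 2rc. Steady inflation, from 6.2% to 11.0% for correlations of 0.1 to 0.5 between a patient's chest and iliac side-differences, would belong to a paired test on 100 matched points. The protocol does not propose that test.

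Nor can side-level randomisation be taken as beyond doubt. The summary literally assigns four parts; the side follows from the methods section and the sample-size count.

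Finally, a rule for combining points could be left to a statistical analysis plan. That would answer a mere omission. Here, however, the protocol itself fixes the comparison and the test, in words that depart from its own design table and sample size. Under the dependence assumed here, the independent test generally misses 5% whichever unit is entered, so the point survives as an inconsistency to correct.

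**Conclusion.** The point holds as an inconsistency about the unit of analysis. Treatment and sample size use the side, item 2 uses compressed parts and contact points, and the summary speaks of four parts assigned. If points are entered, n doubles to 100 per group and the planned test runs at about 2% to 8% in place of 5%. The direction cannot be settled from the protocol. The reported PI rate can move by ten percentage points or more (30% per point against about 41% to 46% per side).

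These sizes rest on assumed correlations and PI rates, and on 50 analysable patients. The difference between the two PI rates needs only that the two points on a side are not perfectly correlated.

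**What to change.** State in item 2 that the unit of analysis is the side, with one outcome per side at each reading: PI at the chest or the iliac crest. Compare it within patient, for example with McNemar's test, and show chest and iliac results separately as description. If contact points are to be modelled, use the GEE already planned in item 3, clustered on patient, with site (chest or iliac crest) as a factor. Either route is valid; choose one before the data are seen.

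Report the PI rate on the same denominator as the test, and reconcile the summary's wording on four randomly assigned parts with the side-level allocation in section 4.

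The cost is a sentence or two in item 2 and one in the summary. Data collection does not change, and the sample size is already counted in sides. With the side-level outcome, the price is that site-specific results become descriptive.
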